### **10.11. Treatment duration**

Patients remain on treatment until one of the following events, whichever occurs first:

- Documented progression according to RECIST v1.1 in chemo-radiotherapy phase
- Documented progression according to RECIST v1.1 in randomised consolidation phase
- Secondary malignancy resulting in need of systemic treatment
- Unacceptable toxicity
- Medical condition that prevents further treatment
- Patient withdraws consent
- Patient becomes pregnant

- One year of maintenance treatment has been completed

Nivolumab and ipilimumab are expected to trigger immune-mediated responses, which require activation of the immune system prior to the observation of clinical responses. Such immune activation may take weeks to months to be evident. Some patients may have objective volume increase of SCLC tumour lesions within 9 weeks following the start of nivolumab and ipilimumab dosing. In some patients, tumour volume or other disease parameter increases may represent infiltration of lymphocytes into the original tumour or blood. In conventional studies, such tumour volume or relevant laboratory parameter increases during the first 9 weeks of the study would constitute PD and lead to discontinuation of imaging to detect response, thus disregarding the potential for subsequent immune-mediated clinical response.

Therefore, patients with tumour volume increase detected up to week 9 of IMP treatment but without appearance of new lesions or rapid clinical deterioration should continue to be treated with IMPs and be clinically observed with a stringent imaging schedule 4 weeks later to allow detection of a subsequent tumour response. This will improve the overall assessment of the clinical activity of IMPs and more likely capture its true potential to induce clinical responses. This must follow the definitions below:

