2.1 Analysis timing

According to the modified statistical design, the final efficacy analysis will be performed when the 81 required PFS events have been observed among all STIMULI patients randomized under AM1.

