2.3 Analysis population

Efficacy cohort: The efficacy cohort is the Intention-to-treat (ITT) population of the trial and includes all randomized subjects under protocol AM1. Patients will be evaluated in the treatment arms to which they were randomly assigned, regardless of the treatment actually received, including patients who were randomized but did not receive any trial treatment.

Safety cohort: The safety cohort consists of all subjects who have received at least one dose of IMP treatment plus all patients randomized to observation arm (under protocol AM1).

Patients will be evaluated according to the treatment they actually received, irrespective of their allocated treatment at randomization.

Per-Protocol cohort: Per-protocol cohort includes all patients enrolled under protocol AM1.

Per-Protocol safety cohort: Per-protocol safety cohort includes all patients enrolled under protocol AM1, who received at least one dose of chemo-radiotherapy after enrollment.

3 Primary efficacy analysis of PFS

Primary efficacy analysis of PFS (primary endpoint) will be performed on **all randomized patients under AM1 protocol, based on their initial treatment assignment (ITT, efficacy cohort)**. PFS time is measured from time of randomization.

Formal hypothesis testing

Based on the protocol AM1 and after the modifications arose from the premature study accrual termination, the trial is designed to test the hypotheses that treatment with chemoradiotherapy and PCI followed by consolidation treatment (nivolumab plus ipilimumab) will lead to an increase in median PFS to 22.8 months, from 13.1 months under treatment with chemoradiotherapy and PCI without consolidation treatment. According to the study design, this corresponds to a PFS HR of 0.57. Using 80% power and a one-sided type I error of 5%, a total of 81 PFS events are needed to observed in order to achieve the trial goal.

In the frame of final efficacy analysis, the **formal comparison** of the PFS between the two treatment arms, will be based on **stratified log-rank test** (with number of fractions of radiotherapy [1/2] and administration of FDG-PET-CT [Yes/No] being the stratification factors). Unstratified log-rank test will be also calculated. This would be of particular value in case at least one stratum level has very low number of patients.

Further PFS analyses

The following **PFS analyses** will also be performed and presented

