- The total number (%) of PFS events observed, overall and by treatment arm will be presented. In addition, 6-month and 1/2-year PFS estimates, median PFS and respective 95% CI will be provided. Respective results by stratifications factors will be also presented.
- Kaplan-Meier plots by treatment arm as well as by treatment arm within each stratification factor will be created.
- Number of PFS events, median PFS and unstratified/unadjusted HRs (along with 95% CI) will be summarized for the **subgroups** defined by the following clinicopathological variables of interest: gender, smoking history, ECOG performance status at randomization, stage of tumour, age (appropriately categorized) and biological markers (if available). This information will be depicted in a tabular format in the report (a corresponding forest plot will be subsequently produced for presentation/publication).

- To assess the effect of trial treatment and other clinicopathological variables on PFS, Cox proportional hazard models will be fitted.

- Initially a univariate (stratified and unstratified) Cox model will be fitted in the model and the statistical significance of trial treatment will be tested at the 5% significance level.
- o Subsequently, multivariate Cox models (stratified and unstratified) will be estimated, adjusted for the clinicopathological variables of interest as defined above (in case of unstratified model, the stratification factors will be also included in the covariates of the model). The backward elimination method, with a removal criterion at 10% will be used to conclude on the statistically significant variables of the model. The HRs along with the corresponding 95% CIs for all significant predictors (in the multivariate Cox model) will be summarized in a tabular format in the report (a corresponding forest plot will be subsequently produced for presentation/publication).
- The proportionality assumption of Cox model will be explored by Schoenfeld's residuals and by testing for time-dependent effect of covariates in extended Cox models. In cases that non-proportionality is detected further appropriate measures will be used
 - Use of variable(s), for which proportionality assumption is violated, as stratification factor(s)
 - Use of weighted tests, alternatives to log-rank for the comparison of survivals, such as the Wilcoxon test

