 - Estimation of Restricted Mean Survival Time (RMST) at specific time points (close to median follow and covering the full follow-up time for the majority of patients)
 - Calculation of HR for separate time intervals

4 Additional secondary analysis

In this section, we present in detail the additional analysis that will be performed in the frame of final efficacy analysis for STIMULI trial.

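### SAP section 3 plans RMST for PFS only if non-proportional hazards are detected, but 81 events give a proportionality test little power against a plausible delayed effect

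*SAP*

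**What the plan says.** SAP section 3 makes the stratified log-rank test the formal PFS comparison, with no condition attached. Under the further PFS analyses, these are also unconditional: event counts, 6-month, 1-year and 2-year PFS, median PFS with 95% CI, Kaplan-Meier plots, and Cox models (stratified and unstratified, univariate and multivariate).

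The check comes next: "The proportionality assumption of Cox model will be explored by Schoenfeld's residuals and by testing for time-dependent effect of covariates in extended Cox models". Then: "In cases that non-proportionality is detected further appropriate measures will be used". Four measures follow: stratifying on the offending variable, weighted tests such as Wilcoxon, "Estimation of Restricted Mean Survival Time (RMST) at specific time points", and "Calculation of HR for separate time intervals". RMST and interval HRs are planned nowhere else. SAP 4.3.1 on OS lists neither of them.

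The SAP gives no test level, time scale or decision rule for detection, and no cut-points for the intervals. The RMST horizon is described only by reference to the follow-up achieved, so it depends on the data.

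On size, SAP section 3 states: "Using 80% power and a one-sided type I error of 5%, a total of 81 PFS events are needed". SAP 2.1 adds that "the final efficacy analysis will be performed when the 81 required PFS events have been observed". On mechanism, Protocol 10.11 says of immune activation: "Such immune activation may take weeks to months to be evident".

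**The concern.** A test that decides whether an estimate is reported should have a reasonable chance of finding the departure it guards against. If it misses a delayed effect, the report carries a Cox HR as its between-arm effect measure. That HR averages a period of no effect with a period of benefit, with weights that depend on accrual and follow-up. RMST, which needs no proportionality assumption, is then not called for.

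When the test does fire, the interval HRs appear only in datasets chosen for a steep time trend. That pushes the early HR up and the late HR down. An inflated early HR could be read as early harm from nivolumab plus ipilimumab and so colour the benefit-risk discussion.

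**Working it through.** **Reproducing the SAP's event count.** Schoenfeld's formula for 1:1 allocation is D = 4(z₁₋α + z₁₋β)² / (ln HR)². The inputs are one-sided α = 0.05 (1.645), power 80% (0.842) and medians of 13.1 and 22.8 months, so HR = 13.1/22.8 = 0.5746, which the SAP rounds ("According to the study design, this corresponds to a PFS HR of 0.57"). D = 4 × 2.4865² / 0.5541² = 80.5, rounded up to 81. This matches. The formula sizes a test of one constant HR. It says nothing about power to detect a changing one.

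**Assumptions that the documents do not supply.**
- Detection is a two-sided 5% test (10% also shown).
- N randomised is 120 to 180. SAP 1.4.2 says only that the number was reduced.
- Accrual is uniform over 40 months (18 December 2015 to 30 April 2019, from SAP 1.6 and 1.4.2).
- The effect is HR 1 for 2 to 6 months, then 0.30 to 0.57.

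**A quick bound.** Take a 3-month delay, then HR 0.50. At N = 130 to 180 the first 3 months hold about 19 to 24 of the 81 events. Suppose the analyst knew the true change-point and compared the log HRs on either side of it. The variance is about 4/d₁ + 4/d₂.
- d₁ = 19, d₂ = 62: variance 0.275, SE 0.524, z = ln 2 / 0.524 = 1.32, power 26%.
- d₁ = 24, d₂ = 57: variance 0.237, SE 0.487, z = 1.42, power 30%.

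So even this favourable contrast misses 70-74% of the time.

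**Simulation.** Control was exponential with median 13.1 months, the experimental arm piecewise exponential, allocation 1:1, with analysis at the 81st event and at least 2,000 trials per scenario. The test was a score test of treatment × g(t) on Schoenfeld residuals, with g = time, event rank or log time. Under proportional hazards it rejected 5-6% of the time, so it is calibrated. Results at N = 150:

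| Delay (months), then HR | Average HR | Missed at 5% (range over g) | Missed at 10% (rank) |
|---|---|---|---|
| 2, 0.57 | 0.63 | 88-92% | 83% |
| 2, 0.50 | 0.57 | 82-89% | 77% |
| 3, 0.50 | 0.60 | 79-86% | 72% |
| 3, 0.45 | 0.56 | 73-82% | 65% |
| 4, 0.40 | 0.56 | 64-75% | 53% |
| 6, 0.57 | 0.74 | 82-84% | 72% |
| 6, 0.40 | 0.63 | 60-68% | 48% |
| 6, 0.30 | 0.56 | 38-48% | 27% |

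Adding 9-week scans for 3- and 6-month delays with late HR 0.57 or 0.40 gives 57-90% missed, so it changes little. A rerun at N = 130 to 180 on the rank scale detected the 3-month, HR 0.50 case in about 19-20% of trials, and missed the 6-month, HR 0.30 case in about 37%.

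**Selection.** For the 3-month delay then HR 0.50, without the gate the interval HRs centre on 1.00 and 0.50. Among trials where the test fires (N = 130 to 180), the medians are 1.40-1.52 early and 0.42-0.43 late.

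**Would a compulsory 0-3 month HR be better?** With 19 to 24 early events and a true HR of 1.00, the SE of the log HR is about √(4/d) = 0.459 to 0.408. The chance of an estimate above 1.4 is 1 − Φ(0.336/0.459) = 23%, falling to 1 − Φ(0.336/0.408) = 20%. Simulation gives about 20-24%. Under the SAP's gate such a value is displayed in about 10-11% of trials. The cut-point matters too: with a true 6-month delay then HR 0.50, a 3-month cut gives a late HR of 0.61.

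**RMST and its horizon.** For exponential PFS, RMST(τ) = (1 − 2^(−τ/m)) × m / ln 2, where m is the median. At the design medians:
- τ = 18 months: 13.86 − 11.61 = 2.3 months.
- τ = 24 months: 17.04 − 13.59 = 3.4 months.

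The size of the difference follows the horizon, so the horizon has to be fixed in advance.

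**The case against.** The strongest reply is that nothing confirmatory is gated. The log-rank test is fixed, and a reader can see a delayed separation in the Kaplan-Meier curves, milestone rates and medians. A between-arm difference in milestone rates can be derived from the two arm estimates. This stands, and it limits the point to supportive output. It does not remove it, because the SAP plans no such difference with a CI and the Cox HR remains the only planned type of between-arm estimate.

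Second, a reader might infer that the SAP treats a non-significant test as proof of proportional hazards. It does not say so. It says that the assumption will be explored, and sets no pass mark.

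Third, a reader might take 60-90% as a general property of the plan. It depends on the assumed test level, delay and late effect, as the table shows. Nor can N = 260 be used: that was the amendment 1 target, and SAP 1.4.2 says the number randomised was reduced.

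Fourth, Protocol 10.11 explains why treatment may continue through early volume increase. It gives no PFS hazard pattern, and the design assumes a single HR of 0.57. A delayed effect is therefore plausible on the protocol's account, not predicted by it.

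Fifth, RMST depends on its horizon, as the HR depends on follow-up. That is true, and it is the reason to fix the horizon beforehand.

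**Conclusion.** The point holds for supportive reporting. With a two-sided 5% test, 81 events and N = 130 to 180, delays of 2 to 6 months followed by an HR of 0.40 to 0.57 are missed in roughly 60-90% of trials. This includes delays of 2 to 4 months whose average HR is close to the design value (64-89%). Misses fall below half for a 6-month delay then HR 0.30, and are fewer throughout at a 10% level. Interval HRs reported only after detection are biased away from each other, materially so in the 3-month example.

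A reader might infer that the primary test or its type I error is compromised. The documents do not support that: the stratified log-rank test does not depend on the proportionality check. A reader might also infer that early-interval HRs should always be shown. The calculation argues against it, because an apparent early harm that does not exist would be displayed about twice as often as under the present rule.

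**What to change.** In SAP section 3, and likewise in SAP 4.3.1 for OS, state that the between-arm RMST difference with 95% CI will always be reported, whatever the proportionality check shows. Fix the horizon in the SAP before the database download. Label the analysis supportive, with no alpha. Treat the Schoenfeld plot and test as descriptive.

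Do not make a 0-3 month HR mandatory. If interval HRs are shown, set the cut-points in advance. State that the early interval holds few events, that the estimates are exploratory and, if the test triggered them, that they are subject to selection.

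The cost is SAP wording and a few lines of code. The event count, alpha and data collection do not change. The downside is one more supportive estimate per endpoint, whose value depends on the chosen horizon.

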4.1 Patient accrual, balance of stratifications factors & baseline characteristics

- A consort diagram will be created to graphically depict the flow of patients and the phases of the trial.
- Patient accrual by center and country will be presented in tabular format (including enrolled, randomized and ineligible patients)
- For patients deemed ineligible a table summarizing the reasons for non-enrolment will be provided¹
- Observed vs. expected accrual over time will be graphically displayed.
- Balance of treatment allocation by center and by stratification factors will be summarized
- Patient and tumour baseline characteristics at enrolment (categorical: gender, smoking history, ECOG performance status at diagnosis, stage (based on 7th TNM classification), TNM stage and continuous: age at enrolment), will be presented for the full cohort of enrolled patients. The same characteristics will be presented for the cohort of randomized patients overall and separately by treatment arm. Note that the ECOG PS reported for the randomized patients is the PS recorded just before the randomization. Frequencies and corresponding percentages will be presented for categorical variables (if missing cases exist, a separate category named "Missing" will be created.), while the following descriptive measures will be considered for the continuous ones: n (non-missing sample size), mean, 95% CI for the mean, median, maximum and minimum values. Balance of baseline characteristics (at randomization) by treatment arm will be assessed via the Fisher's exact test for categorical variables and the Mann-Whitney U test for continuous.
- Available information on medical history will be summarised, by treatment arm.

4.2 Follow-up information and Treatment administration

Follow-up time of the patients will be presented as:

- Median follow-up (FU) of the randomized patients (overall and by treatment arm) along with the respective interquartile range (IQR) and the number (%) of patients that are still on FU.

¹ Note: This table includes the number of patients registered in the database and characterized as ineligible, but this does not represent the full set of screened patients since, it is not mandatory by the protocol to enter in the database all screened patients, even if not eligible.

- A Kaplan-Meier (K-M) plot will be provided for a graphical representation of follow-up time, overall and by treatment arm.

Treatment information will be summarized first for the chemo-radiotherapy phase and then for the randomization phase overall and separately by treatment arm. More specifically the following information will be presented:

- No. of patients enrolled (under protocol AM1)
- No. of patients stopped the trial before starting any treatment
- No. of patients started chemo-radiotherapy treatment
- No. of treatment failures during chemo-radiotherapy treatment (including failure reasons)
- No. of patients completed chemo-radiotherapy phase
- No. of patients not completed PCI for specific reasons
- No. of patients received (and completed) PCI after chemo-radio therapy phase
- No. of unrandomizable patients
- No. of randomized patients (by arm)
- No. of patients that started treatment with the IMP
- No. of patients that completed treatment
- No. and reasons of treatment failures during randomization phase (by arm)
- No. of patients that completed treatment and they experienced a failure afterwards.
- 6-month, 1/2-year TTF rate (%) and median TTF estimates, along with corresponding 95%CI and log-rank test p-value for comparison of the two treatment arms
- A Kaplan Meier curve for TTF by treatment arm
- For those patients who progressed, information on further lines of treatment (if available) will be provided by treatment arm.

4.3 Secondary (efficacy) and exploratory endpoints

4.3.1 Overall survival

Similar to PFS the following will be presented for OS:

- Total number (%) of OS events, overall and by treatment arm (as well as by stratification factor)
- 1-year/2-year OS estimates, median and respective 95% CIs (comparison between treatment arms based on stratified and unstratified log-rank).
- Kaplan- Meier plot by treatment arm

- Subgroup analysis (number of events, median time and unstratified/unadjusted HRs (along with 95% CIs) and variables of interest)

- Univariate and multivariate Cox proportional hazards model, adjusted for the stratification factors and clinicopathological variables of interest; HRs and corresponding 95% CIs for all significant predictors will be presented in a table.
- Summary table of the death causes overall and by treatment arm (e.g., lung cancer, toxicity, other, etc)

4.3.2 Time to treatment discontinuation

- Total number (%) of TTD events, overall and by treatment arm
- 6-month and 1/2-year TTD estimates, median and respective 95% CIs (comparison between the arms based on stratified log-rank).
- Kaplan- Meier plot by treatment arm
- Summary table of the reason of (permanent) treatment discontinuations overall and by treatment arm (e.g., lung cancer, toxicity, other, etc)

4.3.3 Objective response rate

- Overall best responses and objective response rate (ORR) will be presented overall and separately for the two treatment arms, along with a 95% exact binomial CI. ORR will be compared between the two treatment groups using Fisher's exact test and Cochran-Mantel-Haenszel test stratified by the stratification factors of the trial.
- Logistic regression models will be further applied to investigate the treatment effect on ORR, adjusting for stratification factors and variables of clinical interest.
- Note: ORR will be calculated based on the randomized patients who have not attained complete response during chemo-radio therapy.

4.3.4 Graphical illustration of tumour responses

- A waterfall plot will be created by treatment arm to present the best percentage change in tumour size from the baseline tumour assessment before randomization (sum of target lesions diameters).
- The percentage changes in tumour size from the baseline tumour assessment before randomization (sum of target lesions diameters) over the time will be depicted graphically by a spider plot

4.3.5 Duration of response

- Median DOR, along with 95% CI will be presented, for all responders and separately for the two treatment groups.

- Duration of response will be compared between the two treatment arms using the logrank testing and graphically illustrated by Kaplan-Meier curves.
- Graphical representation of duration of response will be also performed via swimmer plot.

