1.1 Objectives and Endpoints

Primary objective

According to protocol AM1, the **primary objective** of the study is to evaluate if patients treated with chemo-radiotherapy and PCI followed by consolidation treatment (nivolumab plus ipilimumab) have a better outcome in terms of progression-free survival (PFS) and overall survival (OS) compared to patients treated with chemo-radiotherapy and prophylactic cranial irradiation without consolidation treatment.

Co-primary endpoints:

- Progression-free survival (PFS) according to RECIST 1.1 criteria based on the local radiologist assessment
- Overall survival (OS)

Important notes:

- Following a subsequent modification in trial design, without requiring protocol amendment, PFS alone was set to be the primary endpoint of the trial, with OS becoming a secondary endpoint. This is further described in section 1.4.2.
- PFS (measured from randomization) are compared between treatment arms only for randomized patients.
- Patients randomized to ipilimumab monotherapy before the protocol AM1, i.e., under the original protocol version, will be excluded from the present final efficacy analysis, and will be evaluated separately.

Secondary endpoints:

- Objective response determined by RECIST 1.1 criteria
- Time to treatment failure (TTF)
- Adverse events graded according to CTCAE v4.0

Exploratory endpoints:

- Time to treatment discontinuation (TTD)
- Duration of response (DoR)

Details on the calculation of endpoints are provided in section 2.2.

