2.2.2 Secondary endpoints

Secondary endpoints include OS, ORR, TTF and adverse events (AEs) graded according to CTCAE v4.0. More specifically:

- OS is defined as the time from the date of randomization until death from any cause.
 Censoring (patients without death) for OS will occur at the last follow-up date.
- ORR is defined as the rate of best overall response (complete or partial response)
 according to RECIST 1.1 criteria across all assessment time-points, during the period from
 randomization to termination of trial treatment. Of note, the determination of ORR will be
 restricted to patients who have not attained a CR during chemo-radiotherapy.
- TTF is defined as the time from the date of randomization to treatment failure for any reason (including progression of disease, treatment toxicity, refusal, lost to follow-up and death). Censoring for TTF (patients without failure) will occur at the last-follow-up date.
- Toxicity, defined as adverse events classified according to CTCAE v4.0.

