2.2.3 Exploratory endpoints

 TTD is defined as the time from the randomization to treatment discontinuation for any reason (including progression of disease, treatment toxicity, refusal, lost to follow-up and death). Censoring for TTD (patients on treatment or completed treatment), will occur at the last-follow-up date

 DoR is defined as the time from the documentation of tumour response (either partial or complete response) to disease progression or death. Censoring will occur at the last tumour assessment with response other than progression.

2.2.4 (Serious) Adverse Events

Adverse Events (AEs)

The main criterion for treatment tolerability is the occurrence of toxicities and adverse events. The severity and causality will be classified according to the NCI CTCAE version 4 (http://evs.nci.nih.gov/ftp1/CTCAE/About.html).

An adverse event is defined as any untoward medical occurrence that occurs from the day of enrolment in the Remote Data Entry (RDE) until 100 days after the final dose of IMP regardless of whether it is considered related to a medication. The relation of the adverse event with the administered trial treatment has to be indicated as: unrelated, unlikely, possible, probable or definite. In addition, any known untoward event that occurs subsequent to the adverse event reporting period that the investigator assesses as possibly related to the protocol treatment should be considered an adverse event.

Immune-related Adverse Events (irAEs)

The following adverse events are of special interest and must be documented after randomization in both treatment arms:

CTCAE Version 4.0 system organ class / preferred terms:

Nervous system disorders:

- Peripheral motor neuropathy
- Peripheral sensory neuropathy
- Meningismus
- Limbic Encephalitis
- Nervous system disorders Other, specify (Guillain-Barré, myasthenia gravis, aseptic or non-infectious meningitis)

Skin and subcutaneous tissue disorders:

- Stevens-Johnson syndrome
- Toxic epidermal necrolysis
- Bullous dermatitis
- Rash acneiform
- Rash maculo-papular
- Pruritus
- Skin and subcutaneous tissue disorders Other, specify

Gastrointestinal disorders:

- Colitis

- Diarrhea
- Colonic perforation
- Small intestinal perforation
- Gastric perforation
- Gastrointestinal disorders Other, specify

Hepatobiliary disorders:

- Hepatic failure
- Hepatitis viral
- Drug-induced liver injury (DILI)

Investigations:

- Alanine aminotransferase increased
- Aspartate aminotransferase increased

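### The exploratory log-rank comparison of duration of response is made among responders only, so randomisation does not protect its p-value, which can mislead in either direction

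*SAP*

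**What the plan says.** SAP 2.2.3 places DoR among the exploratory endpoints and fixes its starting point: "DoR is defined as the time from the documentation of tumour response", ending at progression or death. For patients without an event, "Censoring will occur at the last tumour assessment with response other than progression". SAP 4.3.5 then plans "Median DOR, along with 95% CI will be presented, for all responders and separately for the two treatment groups", followed by the sentence at issue: "Duration of response will be compared between the two treatment arms using the logrank testing", with Kaplan-Meier curves and a swimmer plot. No significance level, sidedness or stratification is given for this test.

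Three other places matter:

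- SAP 2.2.2 counts response only over the period from "randomization to termination of trial treatment". SAP 1.3 gives the observation arm no further treatment.
- SAP 4.3.3 sets the denominator for response: "ORR will be calculated based on the randomized patients who have not attained complete response during chemo-radio therapy". It also compares ORR between arms and fits logistic models for the effect of treatment on ORR.
- SAP 2.3 defines the efficacy cohort, which "includes all randomized subjects under protocol AM1". The primary PFS analysis uses that cohort.

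Neither document warns that responders are selected after randomisation, and neither offers a version of the DoR comparison that keeps all randomised patients.

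**The concern.** A log-rank test between randomised arms is trusted because the groups were alike at the start of follow-up. Here follow-up starts at response, and treatment may affect who reaches that point. The SAP itself treats response as something treatment could change, since it tests and models ORR by arm. If the experimental regimen changes which patients respond, the responder groups differ in prognosis even if it does nothing to duration.

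The setting makes different mixes plausible. Observation-arm responders may be late responders to chemo-radiotherapy. Protocol 4.7 says that response to the study drugs can follow an apparent increase in tumour volume. Protocol 4.2.3 says that response is hard to read on imaging after radiation. The response window in SAP 2.2.2 may also differ by arm: an experimental patient who stops early for toxicity could have a short window, while the observation arm has no treatment to terminate. Protocol 16.8 schedules that arm's end-of-treatment visit around progression or 15 months after randomisation, but the SAP does not say whether this closes its response window.

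At stake is one p-value that could be quoted as showing more durable benefit, or harm, when it reflects who responded.

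**Working it through.** **1. Who enters the test.** DoR needs a documented complete or partial response (SAP 2.2.3), and SAP 4.3.5 reports it for responders. The comparison is therefore responders against responders, selected by a post-randomisation outcome. The PFS comparison is all randomised against all randomised (SAP 2.3 and 3). The ORR restriction is different in kind: complete response during chemo-radiotherapy is known before randomisation, so that exclusion keeps the randomised comparison.

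**2. Check of the event formula on the plan's own figure.** The documents give no figure for DoR. The formula used in step 3 can be checked on the 81 PFS events of SAP 1.4.2 and 3. With 1:1 allocation, one-sided 0.05 and 80% power, events = 4 × (1.645 + 0.842)² / (ln HR)².

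- HR = 13.1/22.8 = 0.5746 gives 81, as stated.
- The rounded HR of 0.57 gives 79.

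**3. Precision of the DoR test.** Solving the same formula for HR gives HR = exp(−2 × (1.645 + 0.842)/√d), where d is the number of progressions or deaths after response. The documents do not give d, so a range is assumed. The one-sided 0.05 level is the one set for PFS, and equal responder numbers per arm are assumed.

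| Assumed events d | HR needed for 80% power |
|---|---|
| 10 | exp(−4.974/3.162) = 0.21 |
| 20 | exp(−4.974/4.472) = 0.33 |
| 40 | exp(−4.974/6.325) = 0.46 |

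This concerns precision only and says nothing about bias.

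**4. Whether bias can arise, and in which direction.** This was simulated on inputs that are all assumptions: 150 patients randomised 1:1; half of good and half of poor prognosis, with median durations of 20 and 6 months; uniform censoring between 6 and 36 months; 4,000 runs; log-rank among responders only, tails at |z| > 1.96.

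| Scenario | Response, control (good / poor) | Response, experimental (good / poor) | Median HR | Experimental better | Experimental worse |
|---|---|---|---|---|---|
| 0: equal response, no duration effect | 30% / 30% | 30% / 30% | 1.01 | 2.8% | 2.7% |
| A: added poor-prognosis responders, no duration effect | 40% / 10% | 40% / 50% | 1.47 | 0.1% | 17.5% |
| B: added good-prognosis responders, no duration effect | 25% / 25% | 65% / 25% | 0.76 | 10.7% | 0.4% |
| C: as A, with true duration HR 0.70 in each class | 40% / 10% | 40% / 50% | 1.12 | 1.4% | 3.7% |

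Overall response in A to C is about 25% against 45%. The mechanism is the mix of responders. In A the good-prognosis share is 0.40/(0.40 + 0.10) = 80% on control and 0.40/(0.40 + 0.50) = 44% on experimental. In B it is 0.25/0.50 = 50% and 0.65/0.90 = 72%.

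With 20,000 patients the hazard ratios for A, B and C were 1.45, 0.77 and 1.10, so the distortion does not fade with sample size. In scenario 0, where treatment does not change who responds, the test behaves properly.

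**The case against.** The strongest reply is that little hangs on this test. DoR is exploratory, is not among the protocol's endpoints, and has no allocated alpha. Formal testing is confined to PFS in the efficacy cohort, and Protocol 18.4 applies no multiplicity adjustment even to the secondary comparisons. That stands and limits the importance of the point. It does not make the comparison valid: an exploratory label warns about multiplicity, not about selection, and a p-value can be quoted without its label.

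It is also fair that the simulation does not size the problem in this trial. It shows that bias is possible in either direction, on invented response rates and prognosis classes. Nor does removing the p-value remove the contrast: medians and curves by arm still place two selected groups side by side, so an explicit statement is needed with them.

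A reader might go further in three ways that the documents do not support:

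- That low power shows bias. It does not; steps 3 and 4 are separate arguments. Low power also limits how often the test would reach significance.
- That observation-arm responses are delayed effects of chemo-radiotherapy. This is plausible, but neither document says so.
- That the ORR restriction in SAP 4.3.3 has the same fault. It does not, because it rests on status before randomisation.

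**Conclusion.** The point holds as a minor one. The planned log-rank test on DoR compares groups formed by a post-randomisation outcome that treatment may change, and the SAP gives neither a caveat nor an all-randomised alternative. Its p-value can therefore mislead in either direction.

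The actual direction and size of the bias cannot be determined from the documents. The simulated hazard ratios illustrate the mechanism and do not predict this trial's result. The test is also likely to be imprecise: for 10 to 40 assumed post-response events, only a hazard ratio of about 0.21 to 0.46 would be detected with 80% power. A reader might infer that the trial's efficacy conclusion is at risk. It is not: PFS and OS are compared in all patients randomised under amendment 1 and do not depend on this test.

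**What to change.** In SAP 4.3.5, delete the between-arm log-rank test. Keep the median with 95% CI, Kaplan-Meier curves and swimmer plot by arm, all already planned, and add a sentence that responders are not a randomised comparison.

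If a comparison of durability is wanted, use the probability of being in response over time in all randomised patients without complete response during chemo-radiotherapy. That is the existing ORR set and is fixed before randomisation. Count non-responders as zero throughout. Define one assessment window from randomisation for both arms, replacing for this analysis the window that ends when trial treatment ends. Protocol 13.2 schedules scans identically in both arms until progression, so no new data collection is needed.

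The cost is one fewer exploratory p-value and, if the alternative is adopted, a short definition and some programming. No sample size or event target changes.
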